8.4 Appropriateness of Measurements

All measurements will be performed using standard methods which are generally recognized as being reliable, accurate, and relevant.

8.5 Primary Efficacy/ Variable(s)

The duration of diarrhea is an appropriate primary efficacy variable. Duration of diarrhea is defined as date and time of the evacuation of the final watery/diarrheal stool before recovery derived from the daily diary.

8.6 Flow Chart of Study Assessments

All study assessments will be conducted as indicated in Table 2, which displays the frequency and timing of all measurements.

Table 2: Flow Chart of Study Assessments

Period	Screening	End of Treatment period	Safety follow-up (phone call 7 days after Visit 2)
Visit	1	2	3
Day	1	6²	11-13
Informed consent	X		
Inclusion/exclusion criteria	X		
Demographic data	X		
Medical history including vaccination history	X		
Physical examination	X	X	
Vitals signs	X	X	
Dispense study drug	X		
Concomitant medication	X	X	X
Compliance check		X	
Global physician assessment		X	
Adverse events	X	X	X
Collect study drug		X	
Dispense diary	X ¹		
Collect diary		X	

¹ Subjects' parent(s)/caregiver(s)/legal representative(s) have to fill in their daily diaries continuously.

² or within 24 hours (in exceptional justified cases within 48 hours) after recovery if this occurs before day 6

9 ADVERSE EVENTS**9.1 Adverse Events**Definition of Adverse Event

Any untoward medical occurrence in a patient or clinical investigation subject administered a pharmaceutical product and which does not necessarily have a causal relationship with this treatment. An AE can therefore be any unfavorable and unintended sign (including an abnormal laboratory finding, for example), symptom (including an AE occurring from drug abuse, an AE occurring from drug withdrawal and any failure of expected pharmacological action), or disease temporally associated with the use of a pharmaceutical product, whether or not considered related to the pharmaceutical product.

An elective surgery/procedure scheduled to occur during a study will not be considered an adverse event if the surgery/procedure is being performed for a pre-existing condition and the surgery/procedure has been pre-planned prior to study entry. However, if the pre-existing condition deteriorates unexpectedly during the study (e.g., surgery performed earlier than planned), then the deterioration of the condition for which the elective surgery/procedure is being done will be considered an adverse event.

9.1.1 Recording of Adverse Events

Any AE should be recorded on the Adverse Events form in the CRF and source documents. In order to avoid vague, ambiguous or colloquial expressions, the AE should be recorded in standard medical terminology rather than the subject's own words. Whenever possible, the Investigator should group together into a single term signs and symptoms which constitute a single diagnosis.

The existence of or change in an AE may be concluded due to the necessity to administer a concomitant medication, from a spontaneous report of the subject, from the physical examination or from special tests like ECG, EEGs, laboratory assessments or other study specified tests (source of AE).

For each subject that has signed the informed consent and prior to study drug allocation at any dose, any change to medical status should be recorded in patient's medical file in accordance to local requirements and the medical history CRF only.

Any change to medical status, which occurs after study drug allocation at any dose in the specified study AE collection period will be handled as an (S)AE.

For each subject that has signed the informed consent but does not qualify for allocation to treatment, i.e. Screen Failure, any change to medical status (from the time of ICF signature until determination of non-qualification for the study) should be recorded in patient's medical file according to local requirements. The related medical status change information will not be reviewed by Abbott or delegated staff, and will not qualify as a study (S)AE.

Each AE, of the treatment arm, is to be evaluated for duration, severity, seriousness and causal relationship to the investigational drug. The action taken with study drug, the concomitant treatment/therapy introduced and the outcome as well as whether the event led to study termination will also be recorded.

The post-study AE collection period is defined as 30 days after the subject's safety follow-up call (collection of (S)AEs should be passive in this period unless otherwise specified).

Severity

The severity of the AE should be characterized as "mild, moderate or severe" according to the following definitions:

- Mild events are usually transient and do not interfere with the subject's daily activities.
- Moderate events introduce a low level of inconvenience or concern to the subject and may interfere with daily activities.
- Severe events interrupt the subject's usual daily activity.

Drug-Event Relationship

The causal relationship between the study drug and the AE should be characterized according to the following:

- Unrelated – there is not a reasonable possibility that the study drug caused the AE.
- Unlikely – suggests that only a remote connection exists between the study drug and the event. Other conditions, including concurrent illness, progression or expression of the disease state or reaction to concomitant medication, appear to explain the AE.
- Possible – suggests that the association of the AE with the study drug is unknown, however the event is not reasonably supported by other conditions.
- Probable – suggests that a reasonable temporal sequence of the AE with drug administration exists and, in the Investigator's clinical judgment, it is likely that a causal relationship exists between the drug administration and the AE, and other conditions (concurrent illness, progression or expression of the disease state, or concomitant medication reactions) do not appear to explain the AE.
- Certain – suggests that an AE, including laboratory test abnormality, occurs in a plausible time relationship to drug administration, which cannot be explained by concurrent disease or other drugs or chemicals. The response to withdrawal of the drug (de-challenge)

should be clinically plausible. The AE must be definitive pharmacologically or phenomenologically, using a satisfactory re-challenge procedure if necessary.

Outcome

The outcome of the adverse event should be classified according to the following definitions:

- Recovered / resolved: the event has resolved (no further symptoms are present and no treatment is being received by the subject).
- Recovered / resolved with sequelae: the event has resolved but there may be lingering effects present (e.g., a scar following a cut or abrasion).
- Fatal: the subject died as a result of the event. This code should only be used for the event that caused the death, not any event that was present at the time of the subject's death. Fatal events require immediately reporting to the Sponsor (or an authorized representative).
- Unknown: may only be used in the event that the subject is lost to follow-up and no reliable data can be obtained.

All efforts should be made to classify the AE according to the above categories.

Note: when the AE is ongoing, the outcome will remain blank on the Adverse Events form in the CRF.

9.1.2 Follow-up of Adverse Events

All AEs occurring during the study are to be followed up in accordance with good medical practice until resolved or judged no longer clinically significant, or if a chronic condition, until fully characterized. All follow-up results are to be reported to the Sponsor (or an authorized representative).

9.2 Serious Adverse Events (SAEs)

Definitions of Serious Adverse Event (SAE)

Any untoward medical occurrence that at any dose:

- results in death,
- is life-threatening (an event in which the subject was at risk of death at the time of the event; it does not refer to an event which hypothetically might have caused death if it were more severe),
- requires inpatient hospitalization or prolongation of an existing hospitalization,
- results in persistent or significant disability/incapacity,
- is a congenital anomaly/birth defect,

-
- is any suspected transmission via a medicinal product of an infectious agent,
 - is considered an important medical event (an event that may not be immediately life-threatening or result in death or hospitalization, but based on medical judgment may jeopardize the subject and may require medical or surgical intervention to prevent any of the outcomes listed above (i.e., death of subject, life-threatening, hospitalization, prolongation of hospitalization, congenital anomaly, or persistent or significant disability/incapacity). Examples of such events include allergic bronchospasm requiring intensive treatment in an emergency room or at home, blood dyscrasia, or convulsions that do not result in inpatient hospitalization or the development of drug dependency or drug abuse as well as spontaneous or elective abortions, stillbirths and ectopic pregnancies).

9.2.1 Reporting Serious Adverse Events

[REDACTED]

[REDACTED]

[REDACTED]

[REDACTED]

[REDACTED]

9.3 Pregnancy

Not applicable due to the age of the subjects.

10 STATISTICAL METHODS AND DETERMINATION OF SAMPLE SIZE

Data handling will be the responsibility of the CRO. The data will be inspected for inconsistencies by performing validation checks. Any inconsistencies found will be resolved by the monitor after contacting the Investigator. When the data in the database are considered clean and the subjects allocated to subject samples in a blind data review, the database will be locked to prevent unauthorized access. Next, the database will be made available as SAS[®] files for statistical analysis.

All details regarding the statistical analysis and the preparation of tables, listings and figures will be described in the Statistical Analysis Plan prepared by the CRO and approved by Abbott before database lock.

The statistical analysis will be performed by the CRO.

10.1 General Definitions and ConventionsTime-Related Definitions

All assessment dates will be related to the first day of study drug administration. This first day of drug administration is referred to as Day 1. Day -1 is the day that is preceding Day 1 and a Day 0 will not be defined.

The baseline period will be defined as the period from informed consent to the first study drug administration. The baseline value for a variable is defined as the last non-missing value collected before the first study drug administration.

The endpoint value for efficacy variables is defined as the last non-missing value assigned to treatment for the subject.

All variables planned to be measured at one or more time points and supposed to be time-related will be windowed.

Coding Systems

AEs and medical history terms will be assigned to a lowest level term (LLT) and a preferred term (PT) and will be classified by high level term (HLT), high level group term (HLGT) and primary system organ class (SOC) according to the MedDRA thesaurus.

Concomitant medications will be classified according to active drug substance using the WHO drug dictionary. The generic name, the preferred name and the WHO name will be assigned.

In addition, the Anatomical Therapeutic Chemical (ATC) classes will be assigned to the drug ID. ATC codes are defined to the 4th level. For each medication, the primary ATC class will be assigned manually based on the generic name and the reason for use.

Default Summary Statistics

The default summary statistics for quantitative and ordinal variables will be the number of observations (n), mean, standard deviation (SD), median, minimum (Min) and maximum (Max) for subjects with data. Any other summary statistics will be described on an individual basis.

Default Frequency Tabulations

For qualitative variables, per category the numbers and frequencies of subjects with non-missing data (n, %) will be the default summary presentation, and if appropriate and present, the number of missing values.

For AEs, medical history and concomitant medications, however, the denominator for the percentage calculation will be the number of subjects at risk ~~for the particular treatment arm~~. A subject will be considered at risk if the subject is in the safety sample and entered the respective study period.

Subject Listings

Individual subject listings will be produced for all raw data and a selection of the derived data.

10.2 Subject Samples

The main subject samples of interest are defined as follows.

The all subjects consented sample will consist of all subjects who:

- Gave their informed consent.

The all subjects <allocated to treatment> sample will consist of all subjects who:

- Were in the all subjects consented sample; and
- Were <allocated to treatment>.

The safety sample will consist of all subjects who:

- Were in the all subjects allocated to treatment sample; and
- Had at least one dose of study medication administered.

The full analysis (FA) sample will consist of all subjects who:

- Were included in the safety sample; and
- Had data for at least one post-baseline assessment of any efficacy measurement.

The per-protocol (PP) sample will be defined through blind data review and will consist of all subjects who:

- Were included in the FA sample; and
- Did not present any major protocol violation.

10.3 Efficacy

The primary efficacy variable is the duration (hours) of diarrhea (treatment duration max 5 days). Duration of diarrhea is defined as date of the evacuation of the last watery/diarrheal stool before recovery or end of treatment.

The primary parameter, duration of diarrhea, will be analyzed using descriptive statistics. In addition, a Kaplan-Meier plot will be generated for which summary statistics will be presented as well.

The secondary efficacy variables are

- Time until recovery, defined as date and time of the evacuation of the first of two consecutive normal stools or no stool within 12 hours after the first normal stool.
- Number of subjects recovered; in total and until each individual treatment day
- Mean and median time until recovery
- Assessment of treatment success by the physician:
The assessment of treatment success by the physician will be done using the Global Physician Assessment.

GPA score:

- 1 = Complete relief of acute diarrhea,
- 2 = marked improvement of acute diarrhea,
- 3 = moderate improvement of acute diarrhea,
- 4 = slight improvement of acute diarrhea,
- 5 = no change in acute diarrhea,
- 6 = worsening of acute diarrhea.

Treatment will be rated as success when the GPA score equals 1 or 2.

- Number of stools at baseline and per treatment day for toilet-trained subjects, only.
- Number of watery stools per day for toilet-trained subjects, only.

Secondary efficacy parameters will be analyzed similarly to the primary analysis. All parameters will also be summarized using descriptive statistics.

10.4 Safety

The safety sample will be used for the analysis of the safety and tolerability data.

AEs are considered treatment emergent (TE) if they start or worsen at or after the first administration of study drug and before or on the day of last administration of study drug plus a gap period of 1 day.

AEs will be reported on a per-subject basis, i.e. counting subjects rather than events. This means that if a subject suffers the same AEs repeatedly during the applicable study period, the event will be counted only once for that period. Repeated events per subject will be summarized according to the following rule: if a subject suffered the same AE more than once, the event will be assigned the worst severity, the closest relationship to the study drug and the earliest starting date. Only treatment emergent AEs will be reported. In the listings, however, all occurrences of the AEs will be presented.

Treatment emergent AEs will be summarized per primary SOC, per HLT by primary SOC and per PT by HLT and primary SOC. Severity and drug-event relationship of treatment emergent AEs are summarized separately. Non-TEAEs will be listed.

Vitals signs, including changes from baseline will be summarized. A frequency table will be presented for markedly abnormal values.

10.5 Other Assessments

The assignment of subjects to subject samples, the disposition of subjects with respect to premature termination, reason for premature termination, drug exposure and treatment compliance will be summarized for the treatment group.

Demographics and other baseline characteristics will be summarized for the treatment group.

Medical history, including coding data will be summarized per primary SOC, per HLT by primary SOC and per PT by HLT and primary SOC.

Major protocol deviations will be listed.

Concomitant medication, including coding data will be summarized per assigned treatment period for incidence per subject, for primary therapeutic subgroup (the 3rd level ATC code) and for generic name by therapeutic subgroup.

10.6 Subgroup Analysis

Key efficacy and safety results will be summarized across subgroups defined by age group (< 24 months old and \geq 24 months old).

10.7 Interim Analysis

Not applicable

10.8 Determination of Sample Size

In total, 40 subjects will be allocated to receive Racecadotril treatment, ~~20 subjects in each age group (< 24 months of age and \geq 24 months of age)~~. Results of a recently finalized study in Russian children showed that all children under Racecadotril treatment recovered within 3 days of drug treatment. A sample size of 40 subjects is sufficient to estimate a two-sided 95% confidence interval with the precision of 3.1 percentage points for a recovery of at least 99% of the subjects after 3 days of Racecadotril treatment. In order to account for drop-outs maximum 48 subjects will be recruited. **Recruitment will be stopped once 40 subjects have completed the study.**

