
summarized. A frequency table will be presented for markedly abnormal values.
 
Sample size
 
In total, 40 subjects will be allocated to receive Racecadotril treatment, 20 subjects in each age group (< 24 months of age and ≥ 24 months of age). Results of a recently finalized study in Russian children showed that all children under Racecadotril treatment recovered within 3 days of drug treatment. A sample size of 40 subjects is sufficient to estimate a two-sided 95% confidence interval with the precision of 3.1 percentage points for a recovery of at least 99% of the subjects after 3 days of Racecadotril treatment. In order to account for drop-outs, maximum 48 subjects will be recruited. Recruitment will be stopped once 40 subjects have completed the study.
		

TABLE OF CONTENTS

CLINICAL STUDY PROTOCOL	1
SYNOPSIS.....	2
TABLE OF CONTENTS	9
LIST OF ABBREVIATIONS AND DEFINITION OF TERMS.....	12
1 ETHICS.....	14
1.1 Independent Ethics Committee or Institutional Review Board	14
1.2 Ethical Conduct of the Study	14
1.3 Subject Information and Consent.....	14
2 INTRODUCTION.....	16
3 STUDY OBJECTIVES.....	17
3.1 Primary Objective(s)	17
3.2 Secondary Objective(s)	17
3.3 Safety Objective(s).....	17
4 STUDY DESIGN.....	18
4.1 Overall Study Design and Plan-Description	18
4.2 Discussion of Study Design, Including the Choice of Control Groups	19
5 SELECTION OF STUDY POPULATION.....	20
5.1 Inclusion Criteria.....	20
5.2 Exclusion Criteria	20
6 REMOVAL OF SUBJECTS FROM THERAPY OR ASSESSMENT.....	21
7 TREATMENTS.....	23
7.1 Treatments to Be Administered	23
7.2 Packaging and Labeling	23
7.3 Storage and Dispensing of Study Drug.....	24
7.4 Method of Assigning Subjects to Treatment Groups.....	24
7.5 Selection of Doses and Timing in the Study	24
7.6 Blinding and Treatment Code Information	24
7.7 Prior and Concomitant Therapy	25
7.8 Treatment Compliance	26

8	STUDY ASSESSMENTS AND FLOW CHART	27
8.1	Efficacy Measurements	27
8.2	Safety Measurements	27
8.3	Other Assessments	28
8.4	Appropriateness of Measurements	29
8.5	Primary Efficacy/ Variable(s)	29
8.6	Flow Chart of Study Assessments	29
9	ADVERSE EVENTS.....	31
9.1	Adverse Events	31
9.1.1	Recording of Adverse Events	31
9.1.2	Follow-up of Adverse Events	33
9.2	Serious Adverse Events (SAEs).....	33
9.2.1	Reporting Serious Adverse Events	34
9.3	Pregnancy.....	34
10	STATISTICAL METHODS AND DETERMINATION OF SAMPLE SIZE	35
10.1	General Definitions and Conventions	35
10.2	Subject Samples	36
10.3	Efficacy	37

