1. INTRODUCTION

This statistical analysis plan (SAP) is based on protocol RACE3002 Version Date 09 OCT 2017, Amendment 1 Date 07 NOV 2018, Amendment 2 Date 22 NOV 2019, TFDA Official Letter (No. 1096009485) dated 08-Jun-2020 as well as Abbott Clarification Letter for Interim Analysis dated 20-Aug-2020. The SAP provides details of data handling procedures, statistical analysis methods for efficacy and safety evaluations. It also outlines statistical programming specifications for tables and listings, and other details on the analyses not provided in the study protocol.

All data of these enrolled and randomized subjects using Protocol Version Date 09 OCT 2017 will be listed only. A note to file (NTF), Racecadotril dosage per sachet dated on 21-Mar-2019 is adapted for Racecadotril dosage collection.

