4.2 Categorical Endpoints

For qualitative variables, per category the numbers and frequencies of subjects with non-missing data (n, %) will be the default summary presentation, and if appropriate and present, the number of missing values. Percentages will be presented with 2 decimals. Partial date(s) will be listed as provided in the listings.

For AEs, medical history and concomitant medications, however, the denominator for the percentage calculation will be the number of subjects at risk. A subject will be considered at risk if the subject is in the safety sample and entered the respective study period.

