4.3 Time-to-event Endpoints

The time-to-event endpoint will be analyzed by Kaplan-Meier method and presented as mean, median and 95% confidence interval for median.

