4.4 Sample Size Estimation and Power

In total, 40 subjects will be allocated to receive Racecadotril treatment. Results of a recently finalized study in Russian children showed that all children under Racecadotril treatment recovered within 3 days of drug treatment. A sample size of 40 subjects is sufficient to estimate a two-sided 95% confidence interval with the precision of 3.1 percentage points for a recovery of at least 99% of the subjects after 3 days of Racecadotril treatment. In order to account for drop-outs 48 subjects will be recruited. Recruitment will be stopped once 40 subjects have completed the study.

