9.2.2 Number of Subjects Recovered

Number and proportion of subjects recovered, in total and until each individual treatment day will be summarized with count and percentage as well as 95% CI as Table 14.2.2 using FA and PP samples.

Subgroup analysis of number and proportion of subjects recovered by age group (< 24 months old and \geq 24 months old) will be also summarized with count and percentage as well as 95% CI as Table 14.2.7 using FA and PP samples.

Subgroup analysis of number and proportion of subjects recovered by weight group (in infants less than 9 kg, in infants from 9 kg to < 13 kg, in children from 13 kg to 27 kg, and in children of more than 27 kg) will be also summarized with count and percentage as well as 95% CI as Table 14.2.12 using FA and PP samples.

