9.2.3 Assessment of Treatment Success by the Physician

The assessment of treatment success by the physician will be done using the Global Physician Assessment.

GPA score:

- 1 =Complete relief of acute diarrhea,
- 2 = marked improvement of acute diarrhea,
- 3 = moderate improvement of acute diarrhea,
- 4 = slight improvement of acute diarrhea,
- 5 = no change in acute diarrhea,

6 = worsening of acute diarrhea.

Individual subject global physician assessment is listed in Listing 16.2.6.3. Treatment will be rated as success when the GPA score equals 1 or 2. The assessment of treatment success by the physician will be summarized with count and percentage as well as 95% CI as Table 14.2.3 using FA and PP samples.

Subgroup analysis of assessment of treatment success by age group (< 24 months old and \ge 24 months old) will be also summarized with count and percentage as well as 95% CI as Table 14.2.8 using FA and PP samples.

Subgroup analysis of assessment of treatment success by weight group (in infants less than 9 kg, in infants from 9 kg to < 13 kg, in children from 13 kg to 27 kg, and in children of more than 27 kg) will be also summarized with count and percentage as well as 95% CI as Table 14.2.13 using FA and PP samples.

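### The 3.1-point precision stated for 40 subjects is a Wald half-width that does not hold near 100% recovery, and the SAP names no interval method for proportions

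*Protocol*

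**What the plan says.** Protocol 10.8 gives the sample-size rationale: "A sample size of 40 subjects is sufficient to estimate a two-sided 95% confidence interval with the precision of 3.1 percentage points". The planning value is recovery of at least 99% of subjects after 3 days. It is supported by an earlier study in Russian children, all of whom recovered within 3 days. The protocol synopsis repeats this, and SAP 4.4 again gives a "precision of 3.1 percentage points for a recovery of at least 99% of the subjects after 3 days of Racecadotril treatment". None of the three places names the formula. Up to 48 subjects may be recruited, and recruitment stops at 40 completers.

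SAP 9.2.2 plans the recovery analysis: number and proportion, "in total and until each individual treatment day will be summarized with count and percentage as well as 95% CI". SAP 9.2.3 plans that physician-rated treatment success "will be summarized with count and percentage as well as 95% CI as Table 14.2.3 using FA and PP". Both repeat this by age group and by weight group. Neither names an interval method.

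The general sections do not supply one. SAP 4.2 says "For qualitative variables, per category the numbers and frequencies of subjects with non-missing data (n, %) will be the default summary presentation" and gives no confidence interval. SAP 4.3 covers time-to-event endpoints only, "presented as mean, median and 95% confidence interval for median".

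**The concern.** A normal-approximation interval for a proportion needs a reasonable number of expected events on both sides. With 40 subjects and 99% recovery, 0.4 failures are expected. A precision figure obtained this way says little about the interval the trial will report.

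Two things are at stake:

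- **The rationale for 40.** This is the only sample-size argument visible in the public documents (Protocol 4.2 is redacted). A reader would expect a tighter interval than the trial is likely to deliver.
- **The reported intervals.** With no method named, the choice could be made after the data are seen, at the boundary where methods differ most. If the Wald formula implied by the 3.1 were carried into the tables, any cell with 100% recovery would show an interval of zero width.

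**Working it through.** **Inputs.** From Protocol 10.8 and SAP 4.4: n = 40, two-sided 95%, assumed recovery p = 0.99, stated precision 3.1 points. All figures use the denominator of 40 from the planning sentence unless stated otherwise.

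**Step 1: reproduce the stated figure.** Wald half-width = 1.96 × √(p(1 − p)/n) = 1.96 × √(0.99 × 0.01/40) = 0.0308, or 3.1 points. Inverted, n = 1.96² × 0.99 × 0.01/0.031² = 39.6, which rounds up to 40. The match is close. Other candidates miss: a one-sided critical value gives 2.6, a continuity correction 4.3, and Wilson evaluated at p = 0.99 gives 5.2.

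**Step 2: check whether the approximation is usable.**

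- Expected failures: 40 × 0.01 = 0.4.
- Limits: 0.99 ± 0.0308 = 95.9% to 102.1%. The upper limit is impossible.
- Coverage: at 40/40 the Wald interval collapses to 100% and misses 0.99. That outcome has probability 0.99^40 = 0.669. Summing over the binomial, the nominal 95% interval covers 0.99 with probability 0.331.

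**Step 3: half-widths at the likely outcomes.** The Clopper-Pearson lower limit is the 0.025 quantile of Beta(x, n − x + 1), and the upper limit is the 0.975 quantile of Beta(x + 1, n − x). At 40/40 the lower limit is 0.025^(1/40) = 0.9119, so the half-width is (1 − 0.9119)/2 = 0.0440.

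| Recovered | Probability at p = 0.99 | Clopper-Pearson 95% CI | Half-width, Clopper-Pearson | Wilson | Jeffreys | Wald (untruncated) |
|---|---|---|---|---|---|---|
| 40/40 | 0.669 | 91.2% to 100% | 4.4 | 4.4 | 3.0 | 0.0 |
| 39/40 | 0.270 | 86.8% to 99.9% | 6.5 | 6.2 | 5.4 | 4.8 |
| 38/40 | 0.053 | 83.1% to 99.4% | 8.2 | 7.6 | 7.0 | 6.8 |

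The first two rows together have probability 0.94. Relative to 3.1, the Clopper-Pearson half-widths are 1.4, 2.1 and 2.6 times as large. Half-width is the kinder summary here, because the interval is lopsided: the lower Clopper-Pearson limit lies 8.8 points below the estimate at 40/40 and 10.7 points below at 39/40.

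**Step 4: average over outcomes at p = 0.99, n = 40.**

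| Method | Expected half-width (points) | Probability half-width ≤ 3.1 | Coverage |
|---|---|---|---|
| Clopper-Pearson | 5.2 | 0 | 0.993 |
| Wilson | 5.1 | 0 | 0.939 |
| Jeffreys | 3.9 | 0.669 (40/40 only) | 0.939 |

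**Step 5: scale.** A Clopper-Pearson half-width of 3.1 or less needs 58 subjects with no failures or 88 with one. The expected half-width at p = 0.99 first falls to 3.1 at n = 79. These numbers show the size of the gap and are not a proposal.

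**Step 6: sensitivity to the denominator.** The documents do not fix the analysed number. The full analysis sample could hold up to 48 subjects; Clopper-Pearson then gives 3.7 points at 48/48 and 5.5 at 47/48, still above 3.1. In the other direction, the per-protocol sample can be smaller. SAP 1 also says "All data of these enrolled and randomized subjects using Protocol Version Date 09 OCT 2017 will be listed only", without saying whether those subjects count toward the 40. Fewer analysed subjects would widen the intervals.

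**The case against.** The strongest reply is that nothing hangs on the figure. The primary variable is duration of diarrhea, analysed descriptively and by Kaplan-Meier. There is no hypothesis test, margin or success rule, and the remedy leaves the sample size alone. This stands, and it limits the point to minor.

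A second reply is that the gap depends on the comparator. Clopper-Pearson is conservative, with about 99% coverage here. Jeffreys gives 3.0 points at 40/40, the most likely result. Since 99% is stated as a floor, 40/40 may be likelier than 0.67: at p = 0.995 it has probability 0.995^40 = 0.82. This stands in part. Wilson is not conservative at this point (94% coverage), yet it agrees closely with Clopper-Pearson and never reaches 3.1. Jeffreys misses 3.1 as soon as one child fails to recover.

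Third, 99% of 40 is 39.6 children, so the planning value cannot be observed exactly; but a planning proportion is an assumed true rate and need not be an attainable count. That is fair, and the conclusion does not rest on it.

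Fourth, the SAP never says that Wald will be used in the tables, so the zero-width interval is conditional. That is also fair. What is certain is that the method is unspecified.

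**Conclusion.** The point holds, as a minor one. The 3.1 points are correctly computed but come from an approximation that is not valid with 0.4 expected failures. At n = 40, neither Clopper-Pearson nor Wilson limits reach that precision at any outcome, and Jeffreys does so only if all 40 recover. On the plan's own assumption of 99%, the Clopper-Pearson half-width is 4.4 or 6.5 points with probability 0.94, and 5.2 on average. Separately, the SAP promises 95% intervals for proportions without naming a method; at 40/40 the lower limit would be 91.2% with Clopper-Pearson or Wilson, 94.0% with Jeffreys and 100% with Wald.

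The sizes assume a denominator of 40 and a true rate of 0.99 for recovery by day 3. No planning value is given for earlier days or for physician-rated success. The effect is confined to the sample-size rationale and the reporting of secondary proportions.

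**What to change.** Keep n = 40.

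- In the synopsis, Protocol 10.8 and SAP 4.4, replace the 3.1-point sentence with: *If 40/40 recover, the exact (Clopper-Pearson) 95% CI is 91.2% to 100%; if 39/40 recover, it is 86.8% to 99.9%.* These limits apply to a denominator of 40.
- In SAP 9.2.2 and 9.2.3, name Clopper-Pearson for Tables 14.2.2, 14.2.3, 14.2.7, 14.2.8, 14.2.12 and 14.2.13. This matches the restated precision and prevents a zero-width interval in any cell at 100%.

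The cost is one sentence in three places and one interval option in the program, with no extra patients. The downside is that the stated precision looks less favourable and that Clopper-Pearson is conservative (99% coverage at p = 0.99 and n = 40, against 94% for Wilson and Jeffreys). If the sponsor prefers Wilson or Jeffreys, the precision sentence should be restated with that method's limits.
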